APPENDIX C: RHEUMATOID ARTHRITIS IMPACT OF DISEASE - RAID QUESTIONNAIRE

Considering
describes y
Very g
7. Coping
Considering
Very w

APPENDIX D: HOSPITAL ANXIETY AND DEPRESSION SCALE (HADS)

Plea

APPENDIX E: FACIT FATIGUE SCALE (VERSION 4)

An16

APPENDIX F: HEALTH ASSESSMENT QUESTIONNAIRE – DISABILITY INDEX (HAQ-DI)

Dr

Hy.

repre:

--	--

APPENDIX G: INTERNATIONAL PHYSICAL ACTIVITY QUESTIONNAIRE (IPAQ)

T

[figure not shown]
APPENDIX H: MULTIDIMENSIONAL ASSESSMENT OF THYMIC STATES (MATHYS)

environn

APPENDIX I: GLOBAL ASSESSMENT OF DISEASE ACTIVITY

Patient global assessment of disease activity

[figure not shown]
Considering all the ways that your rheumatoid arthritis affects you, rate how you are doing on the following scale by placing a vertical mark on the line:

Very
0 m

Physician global assessment of disease activity

Place a vertical mark on the line for how you would assess your patient's current activity:

Very
0 m

**APPENDIX J: POTENTIALLY CLINICALLY SIGNIFICANT ABNORMALITIES (PCSA)
CRITERIA**

Parameter	PCSA	Comments
Chemistry Blood		
Creatinine clearance (Cockcroft-Gault equation) (mL/min)	<15 (end stage renal disease) ≥ 15 - < 30 (severe decrease in Glomerular Filtration Rate (GFR))	FDA draft Guidance 2010
	≥ 30 - < 60 (moderate decrease in GFR) ≥ 60 - < 90 (mild decrease in GFR) ≥ 90 (normal GFR)	Pharmacokinetics in patients with impaired renal function-study design, data analysis, and impact on dosing and labeling
Total Bilirubin	> 1.5 ULN > 2 ULN	Must be expressed in ULN, not in μmol/L or mg/L. Concept paper on DILI – FDA draft Guidance Oct 2007. Internal DILI WG Oct 2008. Categories are cumulative. First row is mandatory. Rows following one mentioning zero can be deleted.
AST (SGOT)	By distribution analysis: > 3 ULN > 5 ULN > 10 ULN > 20 ULN	Enzymes activities must be expressed in ULN, not in IU/L. Concept paper on DILI – FDA draft Guidance Oct 2007. Internal DILI WG Oct 2008. Categories are cumulative. First row is mandatory. Rows following one mentioning zero can be deleted.
	Additional analysis: > 1 – 1.5 ULN > 1.5 – 3 ULN > 3 - 5 ULN > 5 – 8 ULN > 8 ULN	
ALT (SGPT)	By distribution analysis: > 3 ULN > 5 ULN > 10 ULN > 20 ULN	Enzymes activities must be expressed in ULN, not in IU/L. Concept paper on DILI – FDA draft Guidance Oct 2007. Internal DILI WG Oct 2008. Categories are cumulative. First row is mandatory. Rows following one mentioning zero can be deleted.
	Additional analysis: > 1 – 1.5 ULN > 1.5 – 3 ULN > 3 - 5 ULN > 5 – 8 ULN > 8 ULN	
ALT (SGPT) and Total Bilirubin	ALT>3 ULN and Total Bilirubin > 2 ULN	Concept paper on DILI – FDA draft Guidance Oct 2007. Internal DILI WG Oct 2008. To be counted within a same treatment phase, whatever the interval between measurement.
Lipid panel		
Total Cholesterol	≥7.74 mmol/L ≥6.2 mmol/L	Threshold for therapeutic intervention.
LDL Cholesterol	≥4.1 mmol/L ≥4.9 mmol/L	Threshold for therapeutic intervention.
	Triglycerides	
Hematology		
Erythrocytes	≥ 6 x10 ¹² /L	
White blood cells	≥ 16.0 x10 ⁹ /L	

Hemoglobin	≤115 g/L (Male); ≤95 g/L (Female) ≥185 g/L (Male); ≥165 g/L (Female) Decrease from screening visit ≥20 g/L	
Absolute neutrophil count	< 1.0 x10 ⁹ /L	International Consensus meeting on drug-induced blood cytopenias, 1991. FDA criteria.
Absolute eosinophil count	> 0.5 x10 ⁹ /L or > ULN (if ULN ≥ 0.5 x10 ⁹ /L)	Harrison- Principles of internal Medicine 17th Ed., 2008.
Absolute basophil count	> 0.1 x10 ⁹ /L	
Absolute lymphocyte count	< 0.5 x10 ⁹ /L ≥ 0.5 x10 ⁹ /L – LLN > 4.0 x10 ⁹ /L	
Monocytes	> 0.7 x10 ⁹ /L	
Platelets	< 50 x10 ⁹ /L ≥ 50 - 100 x10 ⁹ /L ≥ 700 x10 ⁹ /L	
Vital signs		
Systolic blood pressure	≤ 95 mmHg and decrease from baseline ≥ 20mmHg ≥ 160 mmHg and increase from baseline ≥ 20 mmHg	To be applied for all positions (including missing) except STANDING.
Diastolic blood pressure	≤ 45 mmHg and decrease from baseline ≥ 10 mmHg ≥ 110 mmHg and increase from baseline ≥ 10 mmHg	To be applied for all positions (including missing) except STANDING.
Heart rate	≤ 50 bpm and decrease from baseline ≥ 20 bpm ≥ 120 bpm and increase from baseline ≥ 20 bpm	To be applied for all positions (including missing) except STANDING.
Physical examination		
Weight	≥ 5% increase from baseline ≥ 5% decrease from baseline	FDA Feb 2007.

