### **11.4.3 Analyses of safety data**

All safety analyses will be performed on the safety population using the following common rules:

The following definitions will be applied to laboratory parameters and vital signs

- The potentially clinically significant abnormality (PCSA) values are defined as abnormal values considered medically important by the Sponsor according to predefined criteria/thresholds based on literature review and defined by the Sponsor for clinical laboratory tests, vital signs. These abnormal values will be detailed in the Statistical Analysis Plan that will be validated before the database freezing.
- PCSA criteria will determine which patients had at least 1 PCSA during the on-treatment period, taking into account all evaluations performed during the on-treatment period, including unscheduled or repeated evaluations. The number of all such patients will be the numerator for the on-treatment PCSA percentage.

Death. The following deaths summaries will be generated:

- Number (%) of patients who died by study period (treatment-emergent AEs, on-study) and reasons for death summarized on the safety population
- All AEs leading to death (death as an outcome on the AE CRF/eCRF page as reported by the Investigator), by primary SOC, HLGT, HLT, and PT, showing number (%) of patients sorted by internationally agreed order of SOC and alphabetic order of HLGT, HLT, and PT
- TEAE leading to death (death as an outcome on the AE CRF/eCRF page as reported by the Investigator) by primary SOC, HLGT, HLT and PT showing number (%) of patients sorted by internationally agreed order of SOC and alphabetic order of HLGT, HLT, and PT.

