5.3.2.4. Safety analyses

All AEs (Serious AE (SAE), AE of special interest (AESI), Treatment-Emergent AE (TEAE), AE leading to death, TEAE leading to death) will be presented by System Organ Class (SOC) sorted by internationally agreed order¹ and Preferred Term (PT). A TEAE is defined as an AE occurring in the time from the first injection of IMP up to 14 days after the last injection. In case of AE/TEAE leading to death, cause of death will be provided.

Laboratory safety variables, vital signs and ECG values will be presented at each assessment.

A frequency table of the number and percentage of subjects will be provided for prior and concomitant therapies by therapeutic class (ATC). The table will be sorted by decreasing frequency of anatomic category followed by all other therapeutic classes. In case of equal frequency regarding anatomic categories, alphabetical order will be used.

The following definitions will be applied to laboratory parameters and vital signs

- The potentially clinically significant abnormality (PCSA) values are defined as abnormal values considered medically important by the Sponsor according to predefined criteria/thresholds based on literature review and defined by the Sponsor for clinical laboratory tests, vital signs (PCSA list provided in [Appendix J](#)).
- PCSA criteria will determine which patients had at least 1 PCSA during the on-treatment period, taking into account all evaluations performed during the on-treatment period, including unscheduled or repeated evaluations. The number of all such patients will be the numerator for the on-treatment PCSA percentage.

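### SAP Appendix J lists normal creatinine clearance (90 mL/min or more) among the PCSA criteria, and the five bands together cover every possible value

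*SAP*

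**What the plan says.** Protocol section 11.4.3 introduces the PCSA approach and leaves the thresholds to the SAP: "These abnormal values will be detailed in the Statistical Analysis Plan that will be validated before the database freezing". Appendix J of the SAP is therefore the only operative list.

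SAP section 5.3.2.4 describes PCSA values as "abnormal values considered medically important by the Sponsor". On counting it says "PCSA criteria will determine which patients had at least 1 PCSA during the on-treatment period", and then "The number of all such patients will be the numerator for the on-treatment PCSA percentage".

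For creatinine clearance (Cockcroft-Gault, mL/min), the PCSA column of Appendix J gives five bands:

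- below 15, the entry that opens "<15 (end stage renal disease"
- 15 to below 30, labelled a severe decrease
- 30 to below 60, labelled a moderate decrease
- 60 to below 90, labelled a mild decrease
- 90 and above, the entry that opens "≥ 90 (normal GFR"

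No note marks the last band as a reference category, and no text says which bands enter the numerator.

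**The concern.** A value that the SAP itself calls normal sits in a column that should hold only abnormal, medically important values. The other parameters that can be read in Appendix J leave their normal range unflagged. Platelets are listed below 50, from 50 to 100, and from 700 upwards (×10⁹/L), so values between 100 and 700 meet no criterion. Lymphocytes between the lower limit of normal and 4.0 ×10⁹/L meet none, and neither do AST and ALT at or below the upper limit of normal.

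SAP section 5.1.4 presents blood chemistry as quantitative data only, whereas hematology also gets normal, low and high classes. The PCSA table is thus the only planned categorical output on renal function. If a programmer follows the written rule for this parameter, the resulting percentage cannot separate a cohort with renal decline from one without.

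**Working it through.** The documents state no expected PCSA percentage, so there is no figure to reproduce. The check is whether the bands cover the range, and what the counting rule then returns.

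**Inputs.** Band limits 15, 30, 60 and 90 mL/min (SAP Appendix J). Counting rule of at least one PCSA on treatment (SAP section 5.3.2.4). Serum chemistry at W4, W12, W24, W36, W48 and early withdrawal, with the first sample between D-7 and D-1 (SAP section 1.5). Section 5.3.2.4 gives a numerator but no denominator; I use patients with at least one on-treatment value.

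**Step 1: coverage.** Each band's upper limit is the next band's lower limit, closed below and open above:

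[0, 15) ∪ [15, 30) ∪ [30, 60) ∪ [60, 90) ∪ [90, ∞) = [0, ∞)

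A grid from 0 to 400 mL/min in steps of 0.01 has 400/0.01 + 1 = 40,001 values. Each falls in exactly one band (minimum 1, maximum 1). The bands are exhaustive and do not overlap.

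**Step 2: the rule as written, for the parameter.** Any on-treatment value x lies in some band, so P(at least one PCSA) = 1. With n measured patients the result is n/n = 100%, whatever the true rate of renal impairment. If the safety population were the denominator, the percentage would simply be the share of patients measured.

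**Step 3: top band taken out.** The first unflagged value is 90 mL/min, so a patient is flagged only if some on-treatment value is below 90. The percentage then carries information.

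**Step 4: why the remaining bands must be named.** The documents give no creatinine-clearance distribution. As an illustration only, assume a between-patient mean of 80 to 110 mL/min, between-patient SD 25 to 30, within-patient SD 8, underlying clearance of at least 30 at entry (the exclusion limit in Protocol section 7.2.2) and three on-treatment visits:

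| Bands counted | Patients flagged |
|---|---|
| all five | 100% |
| below 90 | 30% to 74% |
| below 60 | 5% to 30% |
| below 30 | 0.2% to 3% |

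Under the same assumptions 19% to 38% of patients fall in more than one band across the three visits. Separate rows would count these patients more than once unless the SAP says otherwise.

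**The case against.** The strongest reply is that Appendix J is a row-by-row table layout. The comments for bilirubin, AST and ALT say that categories are cumulative and that rows after a zero row may be dropped, which are instructions for separate rows. The comment beside creatinine clearance cites a guidance on pharmacokinetics in renal impairment, which suggests a classification of renal function. Read this way, the five bands are a distribution and no row need be 100%. This is probably the intent, and it stands as a limit on the 100% figure. It does not remove the contradiction: the SAP does not state this reading, and a normal value would still appear under a PCSA heading. For AST and ALT the appendix labels a second block as additional analysis; the creatinine-clearance entry has no such label.

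It can also be said that the definition overrides the list, because a value called normal cannot be an abnormality. That is fair, but it confirms that the two texts conflict and must be reconciled.

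A reader might go further and infer that renal safety cannot be assessed from the planned output, or that an overall count of patients with any laboratory PCSA is driven to 100%. The documents support neither. SAP sections 3.1, 5.1.4 and 5.3.2.4 keep quantitative summaries of creatinine clearance at each assessment, and adverse events are tabulated by SOC and PT. The SAP describes no PCSA count pooled over all laboratory parameters. The adverse event tables are a partial substitute only, since Protocol section 10.4.3 restricts which laboratory abnormalities are recorded as adverse events.

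**Conclusion.** The entry is wrong as written: Appendix J lists a normal result as a PCSA, against the definition in section 5.3.2.4. The 100% figure is exact for patients with an on-treatment value, on the condition that the at-least-one rule is applied to the parameter with all five bands. With separate rows the fault shrinks to a mislabelled normal row and an undefined count for patients who change band.

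Severity is minor. The output is descriptive (Protocol section 11.4.2.3), no efficacy result depends on it, and a pooled 100% would be noticed at once.

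A reader might also infer that only values below 60 mL/min should count. No text in either document supports that cut: the SAP labels 60 to below 90 a decrease too, and the choice is the sponsor's.

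**What to change.** In SAP Appendix J, creatinine clearance:

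1. Relabel the band of 90 mL/min and above as a reference category that does not enter the PCSA numerator.
2. Have the sponsor state which reduced-clearance bands do enter it.
3. State that each patient is counted once, in the worst on-treatment band.
4. Show all five bands as a shift table from the pre-treatment value to the worst on-treatment value. The flow chart schedules no chemistry sample at V2, so name the screening sample (D-7 to D-1) as the pre-treatment value.

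The cost is one table row and one table shell. All values needed are already collected.
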